**Censoring Rules**

| Situation                       |  | Date of event / censoring                           | Censoring |
|---------------------------------|--|---|-----------|
| Radiological PD (RECIST 1.1)    |  | Date of PD  | No        |
| No radiological PD (RECIST 1.1) | If death within 60 days after last tumor response assessment or the randomization (whichever is later) | Date of death (CRF)                                 | No        |
|                                 | If death not within 60 days after last tumor response assessment / No death                            | Date of last tumor response assessment within trial | Yes       |

Special cases which overrule general rules:

|  |   |                       |     |
|--|---|-----------------------|-----|
| No tumor assessment at baseline  | Death within 60 days after date of randomization                | Date of death         | No  |
|  | Death not within 60 days after date of randomization / No death | Date of randomization | Yes |
| No tumor assessment after start of treatment and no radiological PD (RECIST 1.1) | Death within 60 days after date of randomization                | Date of death         | No  |
|  | Death not within 60 days after date of randomization / No death | Date of randomization | Yes |

The last tumor assessment date is defined as the last available and evaluable tumor assessment performed prior to the cut-off date (or prior to EoS, i.e. subjects lost to follow-up or who withdraw consent). If no evaluable tumor assessment is available, this date will be the randomization date.

Imputation methods for estimating missing data:

- For imputing missing parts of dates for the efficacy analyses (except OS) the missing day in a date will be imputed as the 15th of the month, if month and year is documented. If the imputation is earlier than the date of randomization, the day of randomization is taken. In all other cases missing or incomplete dates will not be imputed.

- For imputing missing day of death date, if month and year is available, the day will be imputed by 15, unless this results in a date not later as a date the subject is known to be alive. In that case the date of death will be imputed by the last date known to be alive + 1.

The treatment effect expressed as hazard ratio of cetuximab plus CTX to CTX alone including 95% CI on PFS time will be primarily evaluated using a stratified Cox proportional hazard model, including treatment and the randomization strata (as specified in the IWRS, see Section 7.2): ECOG performance status (0 versus 1) and primary tumor site (oral cavity versus hypopharynx versus others). Each strata will define separate baseline hazard functions (using the 'STRATA' - statement in SAS Proc PHREG), i.e. for the  $i$ -th stratum the hazard function is expressed as:  $h(i;t) = h(i,0;t) \exp(x\beta)$ , where  $h(i,0;t)$  defines the baseline hazard function for the  $i$ -th stratum and  $x$  defines the treatment arm (0=CTX only, 1=CTX + cetuximab) and  $\beta$  the unknown regression parameter.

Ties will be handled by replacing the proportional hazards model by the discrete logistic model (Ties=Discrete option in SAS Proc PHREG). This is a bridging trial; in discussion with Chinese Health Authority, this trial would be regarded as positive if the point estimation of the stratified hazard ratio is less than or equal to 0.77 (retaining at least 50% of the estimated treatment effect of EXTREME trial).

The PFS time of the 2 treatment arms will be described by means of Kaplan-Meier survival curves (product-limit estimates) and associated summary statistics (median PFS time, corresponding two-sided 95% confidence intervals, minimum, maximum, Q1, Q3). Survival estimates at certain time points (3-, 6-, 12-, 18-, 24 months and every 6 months thereafter as applicable), and number of subjects under risk will also be provided. The confidence intervals for the median will be calculated according to Brookmeyer and Crowley (1982) and confidence intervals for the survival function estimates will be derived using the log-log transformation according to Kalbfleisch and Prentice (1980) (conftype=loglog default option in SAS Proc LIFETEST).

The number of events (PD/death) will also be presented within the same table.

An additional table will provide frequencies for events and censoring status by treatment arm according to the following categories:

- Events: Radiological PD based on existing lesions (progressive disease reported for target and/or non-target lesions) / Radiological PD based on new lesions (new lesion(s) is/are reported) / Radiological PD based on existing and new lesions (both progressive disease reported for target and/or non-target lesions and new lesion(s) are reported) / Death within 60 days
- Censoring: Death not within 60 days / Censored at randomization / Lost to follow-up or withdraw consent / Due to data cut-off

Subjects will be considered as “censored at randomization” in case they have no tumor assessment at baseline and no tumor assessment after start of treatment and no radiological PD or death.

They will be considered as censored due to “Lost to follow-up/withdraw consent” in case they have no PD or death before they are lost to follow-up/withdraw consent.

They will be considered as censored “due to cut-off” in case they have no PD or death before the trial data cut-off.

A listing will display information on event and censoring including the following:

- Subject identification number,
- Treatment arm
- Randomization Date
- Last tumor assessment date before cut-off date
- Death date
- Progression date (IRC)
- PFS (IRC): Censoring Flag (Yes/No)/ Description of the Event/Censoring/ PFS (months)

A scatter plot will be produced to compare planned (y-axis) and actual (x-axis) relative day of tumor assessments by treatment arm (2 colors will be used to clearly identify treatment groups). The planned day for EOEA visit will be assigned as the planned day for the last available efficacy assessment visit.

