Tumor assessment: Tumor assessment will be performed according to RECIST version 1.1. The baseline tumor assessment is to be performed during the screening period within 28 days before the start of trial treatment. Computed tomography (CT) or magnetic resonance imaging (MRI) with contrast enhancement is recommended for tumor assessment. Subsequent tumor response evaluations will be assessed every 6 weeks (± 3 days) starting from the randomization day until occurrence of PD regardless of any cycle delay. If treatment is discontinued for reasons other than PD, subjects will continue to have tumor assessments until either PD, the start of a new antitumor treatment, death, the termination of the trial, or loss of follow up, whichever comes first. If symptoms are suggestive of PD, subjects will be evaluated by imaging studies thereafter for documentation and confirmation of the tumor responses. The details of documentation of tumor assessment is described in Section 7.3.1.

Safety follow-up period: All subjects in Arm A and B will be followed up continuously for safety evaluations according to schedule of assessments in Table 1.1 starting from date of first signature of informed consent. A Safety Follow-up visit will be performed 30 days (± 3 days) after the last dose of trial treatment or immediately before starting any new antitumor treatment. During the treatment period, additional safety evaluations will be on a weekly basis (Arm A only) for physical examination, vital signs, documentation of AEs and concomitant medications, and also at the start of each cycle (for both arms) for ECOG performance status, ECG, hematology, biochemistry and urinalysis. Survival data and any information on new antitumor treatments will be collected every 3 months after the EOEA visit until either death, loss of follow up, or the termination of the trial, whichever comes first.

Primary and secondary endpoints: The primary endpoint of this trial is PFS time, as assessed by an IRC. Secondary endpoints include PFS time, as assessed by the Investigator, OS time, BOR rate, DCR, duration of response, and safety (see Section 8).

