7.1.3 Start of Each Cycle Visit (Day 1 of Each 21-Day Cycle)

For all subjects in Arm A and B, the following procedures and investigations will be performed on Day 1 of each 21-day chemotherapy cycle. A visit window of 3 days is acceptable.

- Randomization (for Cycle 1 only, see Section 6.3).
- Physical examination, check of vital signs, and assessment of ECOG performance status (see Section 7.4.4).
- ECG (see Section 7.4.4.4).
- Blood samples collected after fasting for at least 8 hours for safety laboratory assessments (within 3 days before start of next cycle) (see Section 7.4.3).
- Urinalysis (within 3 days before start of next cycle) (see Section 7.4.3).
- Documentation of AEs and concomitant medications.
- Administration of cetuximab (based on BSA) only for subjects in Arm A.
- Administration of cisplatin (cisplatin may be replaced by carboplatin in subsequent cycles if there are cisplatin-related nonhematologic toxicities) and 5-FU (based on BSA) for subjects in Arm A and B.

Note: ECG and laboratory safety results must be available at start of each cycle visit.

Note: If the subject is not able to visit the Investigator for this evaluation or misses the scheduled visits, the Investigator should attempt to contact the subject or the referring physician by appropriate means to determine the subject's well-being.

7.1.4 6-Weekly Evaluation Visit

For all subjects in Arm A and B, the following procedures and investigations will be performed at 6-week intervals starting from the first dose of trial treatment until the EOEA. A visit window of 3 days is acceptable.

- The evaluations which are completed within 7 days at 6-weekly evaluation visit for physical examination/weight; vital sign; ECG; hematology; biochemistry, and urinalysis can be accepted, and these evaluations at 6-weely evaluation visit will be optional.
- Assessment of ECOG performance status (see Section 7.4.4).
- Documentation of AEs and concomitant medications.
- Tumor assessment (see Section 7.3).

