7.3.2 Criteria for Tumor Response Evaluation

Tumor response evaluation will be performed according to RECIST version 1.1 (see Appendix I) by using CT or MRI and other modalities at a 6-week interval starting from the first dose of trial treatment. In the case of symptoms suggesting progression, subjects should be evaluated by imaging thereafter for documentation and confirmation of the tumor responses.

Evaluation of lesions should be based on images obtained by either CT or MRI. The same method of assessment and the same technique should be used to characterize each identified and reported lesion at baseline and during the trial. If a chest X-ray indicates metastatic disease while the subject is enrolled in this trial, a CT of the chest is required for confirmation. All assessments should be provided by the same physician or radiologist if possible during the trial.

Evaluation criteria for possible combination of tumor responses (e.g., target lesion, nontarget lesion, new lesion, and overall response) are provided in Appendix I.

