### Methodology:

This is an open-label, randomized, parallel-group trial. At the end of a 28-day screening period, all eligible subjects will be randomly assigned into treatment Arm A or B in a 2:1 ratio. Subjects in Arm A will receive a maximum of 6 cycles of chemotherapy (cisplatin plus 5-FU) and cetuximab weekly in the absence of progressive disease (PD), as assessed by the Investigator, and unacceptable toxicity. After 6 cycles of treatment, subjects who derive clinical benefit will continue treatment with cetuximab as monotherapy until either PD or unacceptable toxicity. Subjects in Arm B will receive the same chemotherapy regimen as Arm A alone for a maximum of 6 cycles in the absence of PD and unacceptable toxicity.

Tumor assessment will be performed according to Response Evaluation Criteria in Solid Tumors (RECIST) version 1.1. The baseline tumor assessment is to be performed during the screening period within 28 days before the start of trial treatment. Computed tomography (CT) or magnetic resonance imaging (MRI) with contrast enhancement is recommended for tumor assessment. Subsequent tumor response evaluations will be assessed every 6 weeks ( $\pm$  3 days) starting from the randomization day until occurrence of PD regardless of any cycle delay. If treatment is discontinued for reasons other than PD, subjects will continue to have tumor assessments until either PD, the start of a new antitumor treatment, death, the termination of the trial, or loss of follow up, whichever comes first. If symptoms are suggestive of PD, subjects will be evaluated by imaging studies thereafter for documentation and confirmation of the tumor responses.

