### Intention-to-Treat Analysis Set

The intention-to-treat (ITT) analysis set includes all subjects who were randomized to trial treatment. Analyses performed on the ITT analysis set will take into account subjects' allocation to treatment groups as randomized

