### 16.1 Primary Endpoint Analyses

#### 16.1.1 Primary Analysis of Progression Free Survival (PFS)

Analysis Set

- ITT, PP (as sensitivity analysis if less than 90% of ITT)

The primary endpoint of this trial is PFS time as assessed by independent radiology read. IRC will perform *radiology* and *clinical* reviews as described in the IRC Charter. The results of the *radiology* review will be used for the primary analysis.

The PFS time by IRC is defined as the duration (in months) from the date of randomization until first observation of PD (based on imaging as assessed by IRC), or death due to any cause when death occurs within 60 days after the last tumor assessment or the randomization (whichever is later).

Any subject with neither assessment of tumor progression, nor death date within 60 days after last tumor assessment or randomization will be censored on the date of last tumor assessment or randomization. A subject who has not received trial treatment and for whom no date of progression or death is known will be censored on the date of randomization (Day 1) or date of last tumor assessment, whichever comes later. The following censoring rules will be applied.

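### SAP 16.1.1 gives conflicting PFS censoring rules for randomized, never-treated subjects who were scanned without progression, and the documents disagree on when imaging starts

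*SAP*

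**What the plan says.** **Estimand frame.** SAP 16.1.1: "The PFS time by IRC is defined as the duration (in months) from the date of randomization until first observation of PD". SAP 10.2: "The intention-to-treat (ITT) analysis set includes all subjects who were randomized to trial treatment". Subjects who are randomized but never dosed therefore belong to the primary analysis.

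**Text rule.** SAP 16.1.1, like Protocol 8.3.1 and 8.5.2, counts a death as an event if it falls within 60 days of the last tumor assessment or of randomization, whichever is later. An untreated subject with no known progression or death "will be censored on the date of randomization (Day 1) or date of last tumor assessment, whichever comes later".

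**Table rule.** The censoring table in SAP 16.1.1 then lists special cases that take precedence over the general rules. One is headed "No tumor assessment after start of treatment and no radiological PD (RECIST 1.1". Under it, death within 60 days of randomization is an event; anyone else is censored at randomization.

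**A third definition.** Later in SAP 16.1.1, the category for subjects censored at randomization requires all of these together: no baseline assessment, no assessment after treatment start, and neither radiological PD nor death. The table treats the first two as separate rows, each sufficient alone.

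**Imaging anchor.** Protocol 7.3.2 places scans "at a 6-week interval starting from the first dose of trial treatment", and 7.1.4 "at 6-week intervals starting from the first dose of trial treatment until the EOEA"; the synopsis and the tumor-assessment footnote to Table 1.1 also use first dose. Protocol 5.1 has "every 6 weeks (± 3 days) starting from the randomization day", and SAP 6 "starting from the randomization day until occurrence of PD".

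**The concern.** The row is keyed to an event, start of treatment, that some ITT subjects never have. For such a subject every scan fails to be a scan after treatment start. The row then discards progression-free follow-up that the text keeps, and discards some deaths that the text counts. Two programmers following the same SAP could build different primary datasets.

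Untreated subjects are foreseen: SAP 12.1 counts them by arm and SAP 10.2 lists them as a per-protocol exclusion. The trial is open-label, so their share could differ between arms. Success is a bare point estimate, a stratified hazard ratio of 0.77 or less, with no hypothesis test, so a systematic shift goes directly into the decision. Investigator PFS (SAP 16.2.1) uses the same censoring rules, and follow-up duration (SAP 16.3) inverts them.

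The anchor conflict adds to this. Under the first-dose wording a never-dosed subject has no defined scan date, so whether scans exist at all depends on which section a site follows.

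**Working it through.** **The plan's own figure.** The protocol quotes a 46% PFS risk reduction in the reference trial, a hazard ratio of 0.54. Retaining half of it on the linear scale gives 1 − 0.5 × (1 − 0.54) = 0.77, so the threshold reproduces. With 144 events and 2:1 allocation, SE(log HR) ≈ 1/√(144 × 2/3 × 1/3) = 1/√32 = 0.177.

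**The two rules applied to an untreated subject.** Days count from randomization. Durations use the SAP 11 convention (difference + 1). A clean scan is one without PD.

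| Course | Text rule | Row, read literally |
|---|---|---|
| No scan, alive | censored, 1 day | censored, 1 day |
| Clean scan day 42, alive | censored, 43 days | censored, 1 day |
| Clean scans days 42 and 84, alive | censored, 85 days | censored, 1 day |
| Clean scan day 42, death day 50 | event, 51 days | event, 51 days |
| Clean scan day 42, death day 80 | event, 81 days (80 − 42 = 38 ≤ 60) | censored, 1 day (80 > 60) |
| Clean scans days 42 and 84, death day 130 | event, 131 days (130 − 84 = 46 ≤ 60) | censored, 1 day (130 > 60) |
| PD on day 42 scan | event, 43 days | event, 43 days |

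The rules part only for untreated subjects who were scanned and had no radiological PD. Within that group, the deaths lost are those more than 60 days after randomization but within 60 days of a clean scan.

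**Imaging anchor.** Protocol 6.3 puts randomization on the day of first dose, or one day before it with tetracycline prophylaxis. For treated subjects the anchors differ by 0 or 1 day, inside the 3-day window. Only never-dosed subjects lack a scan date under the first-dose wording.

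**Size.** The documents give no untreated share, so it was varied.
- From the documents: 240 subjects at 2:1 (160/80), control median PFS 3.3 months, 6-weekly scans, true hazard ratio 0.77 (set at the threshold).
- Assumed: exponential PFS; untreated subjects in either arm at the control hazard; 15% of first events are deaths; follow-up uniform from 120 to 600 days; untreated subjects scanned at most 1 or 3 times; unstratified Cox model; 1,500 replicates. This yields about 189 to 194 events, more than the 144 that trigger the analysis.

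| Untreated, Arm A / Arm B | Expected subjects, A / B | HR under row ÷ HR under text (1 scan; 3 scans) | Mean events lost (1 scan; 3 scans) |
|---|---|---|---|
| 1% / 1% | 1.6 / 0.8 | 1.000; 1.000 | 0.07; 0.14 |
| 1% / 3% | 1.6 / 2.4 | 0.996; 0.993 | 0.10; 0.23 |
| 1% / 5% | 1.6 / 4 | 0.992; 0.986 | 0.13; 0.32 |
| 2% / 10% | 3.2 / 8 | 0.984; 0.971 | 0.29; 0.61 |

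The direction follows from the row: it keeps radiological PD as an event but drops event-free time, which raises the apparent hazard in the arm with more untreated subjects. If that is Arm B, the estimate moves toward cetuximab. In the largest case a text-rule estimate of up to 0.77/0.971 = 0.793 would meet the threshold under the row. The shift on the log scale is ln(0.971) = −0.029, about one sixth of the standard error (0.029/0.177 = 0.16).

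**The case against.** The best defense is that the row need not be read this way. The sentence on untreated subjects is itself specific, the row overrules only general rules, and it presupposes a start of treatment, so it can be read as not reaching never-dosed subjects. That stands as far as it goes: the outcome is ambiguous, not fixed. But the plan does not say which rule prevails, and SAP 9 declares no change from the protocol, so the departure looks unintended.

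The affected group is also likely to be very small. A subject must be untreated, still scanned and free of PD, yet randomization is at most one day before dosing and scans stop when new antitumor treatment starts. SAP 12.1 and 16.1.1 plan counts of untreated subjects, a randomized-versus-treated cross-tabulation and a listing of last assessment and death dates, which would expose any case. The sensitivity analysis counting all deaths would recover the lost deaths, though not the lost scan follow-up. These points limit the size; they do not remove the conflict.

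A reader might infer that the plan removes every untreated subject at time zero, so that the primary estimate compares treated subjects only. The documents do not support that: radiological PD and deaths within 60 days of randomization remain events, and subjects without scans are handled identically under both rules. Nor can one say outright that untreated subjects have no scans due, since Protocol 5.1 and SAP 6 start imaging at randomization. Nothing in the documents shows that non-treatment would concentrate in Arm B.

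**Conclusion.** The contradiction is real and lies in the derivation of the primary endpoint. For untreated, scanned, non-progressed subjects, the table row read literally gives a result that conflicts with the SAP's own text and with the protocol. The definition of the censored-at-randomization category agrees with neither the table nor the text, and the imaging anchor is inconsistent across sections.

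The expected effect is small: on average fewer than 1 event lost and about 0 to 3% in the hazard ratio for untreated shares up to 2% in Arm A and 10% in Arm B, with no material change at about 1% per arm. These figures rest on assumed shares, scan counts and a control-level hazard in untreated subjects; a different hazard would change them. The case for correction is an unambiguous primary dataset before a point-estimate decision, not a large expected bias.

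**What to change.** 1. In the SAP 16.1.1 table, reword the row to *No evaluable tumor assessment after randomization and no radiological PD (RECIST 1.1)*. Untreated subjects with scans then follow the general rule, as the text and the protocol intend.
2. Align the definition of the censored-at-randomization category with the table, so that either special case is sufficient and the condition refers to randomization.
3. Use randomization as the single imaging anchor in the protocol synopsis, the Table 1.1 footnote, 7.1.4 and 7.3.2, matching Protocol 5.1 and SAP 6. The planned-visit sensitivity analysis in SAP 16.1.2 then also has one defined set of planned dates.

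The cost is one table row, one definition and four protocol phrases, to be settled before database lock. The only operational consequence is that the few subjects who never start treatment are asked to attend scans already in the schedule.

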8.5.2 Analysis of Primary Endpoint

The primary endpoint of this trial is PFS time as assessed by IRC.

The PFS time by IRC is defined as the duration (in months) from the date of randomization until first observation of PD (based on imaging as assessed by IRC), or death due to any cause when death occurs within 60 days after the last tumor assessment or randomization (whichever is later). Any subject with neither assessment of tumor progression, nor death date within 60 days after last tumor assessment and randomization will be censored on the date of last tumor assessment or randomization. A subject who has not received trial treatment and for whom no date of progression or death is known will be censored on the date of randomization (Day 1) or date of last tumor assessment, whichever comes later.

The analysis will be performed on the basis of the ITT principle on the ITT population.

The treatment effect expressed as hazard ratio of cetuximab plus chemotherapy to chemotherapy alone including 95% CI on PFS time will be primarily evaluated using a stratified Cox proportional hazard model, including treatment and the randomization strata (as specified in the IWRS), ECOG performance status (0 versus 1) and primary tumor site (oral cavity versus hypopharynx versus others).

This is a bridging trial; in discussion with Chinese Health Authority, this trial would be regarded as positive if the point estimation of the stratified hazard ratio is less than or equal to 0.77 (retaining at least 50% of the estimated treatment effect of EXTREME trial, see Section 8.1).

The PFS time of the 2 treatment arms will be described by means of Kaplan-Meier survival curves (product-limit estimates) and associated summary statistics (e.g., median PFS time, 95% CI, survival estimates at certain time points, and number of subjects under risk).

Secondary Analyses of Primary Variable

All secondary analyses of the primary variable will be performed to support the robustness of the primary confirmatory analysis and regarded as exploratory. Such analyses will comprise:

Sensitivity Analyses.

Sensitivity analysis will be employed to explore the robustness of the primary confirmatory analyses to assess the impact of analysis populations, the validity of model assumptions by

- Executing per-protocol analysis. If PP population includes more than 90% of the ITT population, additional efficacy analyses on the PP population will be omitted.

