## 9 Changes to the Planned Analyses in the Clinical Trial Protocol

Not Applicable.

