### 16.1.2 PFS Sensitivity Analyses

To assess the robustness of the primary analysis, the following analyses can be conducted:

- Per-protocol analysis: the same analysis as described above Section 16.1.1 will be repeated on PP analysis set only if PP analysis set includes less than 90% of the ITT analysis set.
- The same analysis as described above Section 16.1.1 will be repeated using results of the *clinical* review from IRC, corresponding listing will also be produced.
- The same analysis as described above Section 16.1.1 will be repeated considering all death as event.
- The same analysis as described above Section 16.1.1 will be repeated considering all death and start of new anti-cancer treatment as event.
- To address the bias due to different times of assessment of disease progression caused by different treatment schedules, the same analysis as described above Section 16.1.1 will be repeated considering date of planned imaging visits instead of date of actual imaging visits. If an event is observed between two planned visits, it will be assigned to the previous one. The planned day for EOEA visit will be assigned as the planned day for the last available efficacy assessment visit.
- The same analysis as described above Section 16.1.1 will be repeated excluding subjects who met the inclusion criteria 3 as defined in protocol version 1.0 (17 November 2014) but who do not meet the updated inclusion criteria 3 as defined in protocol version 2.0 (20 April 2016). Please refer to [Appendix 2](#) for the details for inclusion criteria 3.
- The same analysis as described above Section 16.1.1 will be repeated based on the stratification factors based on eCRF data instead of IWRS data.

Results of PFS primary and sensitivity analyses (hazard ratio and 95%CI) will be displayed using a forest plot.

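### Ties=Discrete replaces the protocol's Cox model, yet the result is still called a hazard ratio: negligible for the 0.77 decision, visible in the planned-visit analysis

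*SAP*

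**What the plan says.** Protocol 8.5.2 says the PFS effect is "primarily evaluated using a stratified Cox proportional hazard model, including treatment and the randomization strata", and reports it as a stratified hazard ratio. It gives no method for ties.

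SAP 16.1.1 repeats this and writes the proportional hazards formula with a separate baseline hazard for each stratum. The next paragraph begins: "Ties will be handled by replacing the proportional hazards model by the discrete logistic model (Ties=Discrete option in SAS Proc PHREG". It goes on to the decision rule: "this trial would be regarded as positive if the point estimation of the stratified hazard ratio is less than or equal to 0.77".

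SAP 16.1.2 introduces the sensitivity analyses with "the following analyses can be conducted". One of them is the 16.1.1 analysis "repeated considering date of planned imaging visits instead of date of actual imaging visits", with the rule "If an event is observed between two planned visits, it will be assigned to the previous one". The section ends: "Results of PFS primary and sensitivity analyses (hazard ratio and 95%CI) will be displayed using a forest plot".

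SAP Section 9, "Changes to the Planned Analyses in the Clinical Trial Protocol", says only that it is not applicable.

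**The concern.** The Cox and discrete logistic likelihoods coincide at event times that are untied within a stratum. At tied times they estimate different quantities: a hazard ratio under Cox, a conditional odds ratio under the discrete model. When treatment works, the odds ratio lies further from 1.

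Ties are expected here because scans fall every 6 weeks (±3 days). They come from recording a continuous progression time at scan dates, which is the situation the Efron and exact methods address. The discrete model treats time itself as discrete.

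Two things could be affected. The first is the primary point estimate, which alone decides whether the trial is positive. The second is the planned-visit analysis, which exists to show bias from different assessment times. If it moves because of the tie option, a reader of the forest plot may take an artefact for robustness or for a stronger effect.

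**Working it through.** **Inputs from the documents.** 240 subjects, 2:1; 144 IRC PFS events (SAP Sections 6 to 8); six strata (ECOG 0/1 by three tumor-site groups); scans every 42 days ±3 days (Protocol 5.1); EXTREME control median 3.3 months and 46% risk reduction (Protocol 3.7.2); 30.4375 days per month (SAP Section 11).

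**The plan's own figure.** Retaining half of a 46% risk reduction gives 1 − 0.5 × 0.46 = 0.77. The threshold is reproduced on the hazard-ratio scale.

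**Closed form with all events on the 6-week grid.** Let H = (ln 2 / control median) × 42 / 30.4375 be the control cumulative hazard per interval. The control event probability is 1 − exp(−H). A hazard ratio HR then corresponds to the odds ratio (exp(HR × H) − 1) / (exp(H) − 1).

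| Control median (months) | H | Control event probability | Odds ratio at HR 0.77 | Odds ratio at HR 0.54 |
|---|---|---|---|---|
| 3.3 | 0.2898 | 0.2516 | 0.744 | 0.504 |
| 4.0 | 0.2391 | 0.2127 | 0.748 | 0.510 |
| 5.0 | 0.1913 | 0.1741 | 0.753 | 0.516 |

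At HR 0.77 the shift on a full grid is 0.77 − 0.753 = 0.017 to 0.77 − 0.744 = 0.026.

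**Simulation.** The Efron and discrete stratified likelihoods were fitted to the same data sets of 160:80 subjects, cut off at the 144th event, with censoring at the last scan. Because the sample-size text is redacted, these inputs are assumed:
- exponential times, with control medians of 3.3, 4.0 and 5.0 months;
- 10% of events are deaths on exact days;
- uniform accrual over 20 months;
- stratum shares of 8/6/6/32/24/24%.

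For the planned-visit data, scheduled scans were set to their nominal day, and deaths and unscheduled scans to the previous planned visit. There were 2,000 replicates at HR 0.77 and ±3 days for 3.3 and 5.0 months, and 1,000 for every other scenario.

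Primary estimate at HR 0.77, mean of discrete minus Efron:

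| Scenario | Events tied within stratum | Mean difference | Trials changing side of 0.77 |
|---|---|---|---|
| 3.3 months, ±3 days | 44% | −0.0032 | 1.0% |
| 4.0 months, ±3 days | 41% | −0.0026 | 0.8% |
| 5.0 months, ±3 days | 38% | −0.0021 | 0.6% |
| 3.3 months, 30% of progressions found by symptom-driven scans | 30% | −0.0019 | 0.5% |
| 3.3 months, ±7 days | 28% | −0.0016 | 0.9% |
| 3.3 months, scans clustered at nominal day (SD 0.6 day) | 65% | −0.009 | 2.5% |

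For scale, SE(log HR) is about 1 / sqrt(144 × 2/3 × 1/3) = 0.18. At HR 1.0 there is no systematic shift (mean difference 0.0005).

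Planned-visit analysis at ±3 days, discrete minus Efron: −0.025, −0.021 and −0.016 at 3.3, 4.0 and 5.0 months for HR 0.77 (87-90% of events tied). For HR 0.54 it is −0.037 at 3.3 months and −0.024 at 5.0.

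Planned-visit minus primary estimate, with no timing bias in the data:

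| Scenario | Discrete: mean (SD) | Efron: mean (SD) |
|---|---|---|
| HR 0.77, 3.3 months | −0.021 (0.030) | 0.001 (0.025) |
| HR 0.77, 5.0 months | −0.014 (0.022) | 0.000 (0.019) |
| HR 0.54, 3.3 months | −0.031 (0.018) | 0.001 (0.016) |

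**Cross-check.** A separately built simulation with 15% deaths gave 0.002 to 0.003 for the primary shift and 0.018 to 0.030 for the planned-visit shift. In it, the planned-visit estimate changed side of 0.77 in about 5-7% of trials.

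**The case against.** The protocol is silent on ties, and filling in such detail is what a SAP is for. The option is disclosed, named and fixed in advance, so it is arguable whether it belongs in Section 9. Most primary events (56-62% in the main runs) are untied, and the estimate is within 0.003 of Efron against a standard error of about 0.18 on the log scale. Calling it a hazard ratio hardly misleads. The changes of side were simulated at a true HR of 0.77, the worst case; in the separate simulation at HR 0.54 none occurred in 500 trials. The planned-visit analysis is exploratory, optional and without a decision rule. Its mean offset at HR 0.77 is smaller than its single-trial SD, so in one trial it could not be told from chance. Once events sit on a 6-week grid, a discrete-time model is coherent, and a corrected label would be enough.

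Much of this stands and keeps the point minor. It does not remove the inconsistency: by the SAP's own wording the proportional hazards model is replaced, while the hazard-ratio label stays. The offset is systematic, favors cetuximab when cetuximab works, and appears in the analysis meant to detect bias. At HR 0.54 and 3.3 months it is about 1.7 SD (0.031 / 0.018). Relabelling alone would still put an odds ratio beside near-hazard ratios in one forest plot.

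The protocol also counts scans from randomization in 5.1 but from first dose in 7.1.4 and 7.3.2. Moving Arm A scans one day later left the planned-visit gap at −0.025.

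**Conclusion.** The concern holds and is minor. For the primary analysis the average effect is 0.002 to 0.003 and the 0.77 decision is practically unaffected: 0.5-1% of trials change side, or about 2-2.5% if scans cluster tightly at the nominal day. The effect that matters is the 0.016 to 0.025 shift in the planned-visit analysis, which makes it look more favorable than the primary result with no timing bias present. Efron removes that systematic offset but not the single-trial noise, whose SD is about 0.02-0.03 at HR 0.77 under either method.

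These sizes assume Efron as comparator, scans spread over ±3 days, and the control medians, death share, accrual and stratum shares listed above. Against Breslow the shifts are roughly twice as large (0.004-0.006 and 0.032-0.054). Nothing is claimed about the tie method used in EXTREME or the scale on which 0.77 was agreed with the authority.

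**What to change.** Before database lock, replace the ties sentence in SAP 16.1.1 with: Ties will be handled with the Efron method (TIES=EFRON); TIES=EXACT will be run as a check. Apply it to the primary PFS analysis, all PFS sensitivity analyses and investigator-assessed PFS. OS follows through its cross-reference to 16.1.1 and is numerically unaffected (0.8005 against 0.8002 with deaths on exact days).

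If a discrete-model result is kept, report it as supportive, label it an odds ratio in tables and in the forest plot, and record the change of model in SAP Section 9.

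The cost is one sentence and one SAS option. The reported ratio may be slightly less favorable.
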